## Study Objectives

Rise for Health will examine 3-month changes in biomarkers of healthy aging and physical, emotional, and cognitive functioning across a 3-arm randomized trial: (1) healthy living attention control (Healthy Living), (2) reduce sitting time (Reduce Sitting), and (3) increase sit-to-stand transitions (Increase Transitions). The study aims to enroll 405 postmenopausal women into the 3-month trial. The primary aim is to compare changes in glucoregulatory biomarkers (fasting plasma insulin and glucose, HbA1c, and HOMA-IR) and blood pressure over 3 months for the 2 intervention arms compared with the attention control condition. We hypothesize that, compared with those allocated to the attention control arm, participants in the 2 intervention arms will have greater improvements in glycemic control and blood pressure. In addition, we will evaluate the dose-response effects of sitting behavior changes on glucoregulatory biomarkers and blood pressure. We hypothesize that greater improvements in the target behavior will be associated with greater improvements in glucoregulatory biomarkers and blood pressure. The secondary aims of the study are to examine the effects of the intervention on physical, emotional, and cognitive functioning. This project will also explore (1) the modifying effects of age on the relationship between the 3 conditions and primary and secondary outcomes, (2) the psychosocial and mediators and moderators of changes in sitting behaviors, and (3) the differences in outcomes between the 2 sitting interruption intervention arms. The purpose of this paper is to describe the study protocol of Rise for Health, a 3-arm randomized trial, to assess ways of interrupting sitting in postmenopausal women.

The institutional review board of the University California San Diego (UC San Diego) approved all study procedures, and all participants will provide written informed consent. Study recruitment, participant safety, and progress are reviewed semiannually by an external independent data safety monitoring board appointed by the National Institutes of Health (NIH).

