#### Objective Measure of Sitting Time and STS Transitions

Measures used to examine the dose-response effects of behavioral changes on glucoregulatory biomarkers and blood pressure are activPAL and ActiGraph GT3X+. For 7 days before the baseline and 7 days before the 3-month final visit, participants are asked to wear the 2 devices for 24 hours a day. activPAL is a small and

lightweight accelerometer worn on the anterior aspect of the thigh that produces a signal related to thigh inclination, which is used to estimate the time spent in different body postures (sitting and standing) and the number of sit-to-stand transitions. activPAL has demonstrated good reliability and validity. activPAL data will be downloaded using activPAL Professional Research Edition software package using the 15-second Epoch. To filter nighttime sleeping, participants are asked to keep a sleep log each night they wear the activPAL. ActiGraph GT3X+ is a small device attached to a belt, positioned over the right hip. The ActiGraph collects data on 3 axes at 30 Hz to estimate the minutes spent in sedentary, light, moderate, and vigorous activity using calibration thresholds. ActiGraph has been validated against heart rate telemetry and total energy expenditure. Nonwear time will be classified using Choi algorithm with 90 consecutive zero counts on the x-axis. We will use the newly validated OPACH cut points to assess moderate PA. In addition, data will be provided to the Biostatistics Core and project 3 for further analysis of bouts, time of day, and clustering with sleep and to validate the machine-learned algorithms.

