Sedentary Behavior Interrupted:
A Randomized Trial of 3-Month Effects on
Biomarkers of Healthy Aging and Physical
Functioning in the Real World (P2)

NCT03473145

August 26, 2025

Statistical Plan

Baseline characteristics were compared across the 3 treatment arms using ANOVA for continuous variables and χ^2 or Fisher exact tests for categorical variables. Study-related adverse events were tabulated by group using a standard medical dictionary for regulatory activities body system categories.

The primary analysis comparing the sit less and sit-to-stand interventions with the healthy living controls used the intent-to-treat principle. Linear mixed models (LMMs) were applied, allowing for the inclusion of partially complete records, thereby reducing complete case analysis biases. The model included baseline and 3-month outcomes as dependent variable; time (baseline, 3-month), group (active, control), and the group*time interaction were fixed-effect independent (categorical) variables. A subject-specific (random) intercept was included to model individual heterogeneity in outcomes. A significant group*time interaction indicated that outcome changes differed between that intervention and the control arm; this difference of outcome changes between intervention and control arms represents the intervention effect.

To reduce the chance of false positives, we first fit the aforementioned LMMs for 2 primary composite outcomes: (1) glucoregulatory outcomes defined as the average of 4 Z scores of insulin, glucose, HbA1c, and HOMA2-IR; and (2) blood pressure composite defined as the average of 2 Z scores of systolic and diastolic blood pressure. The Z score for each participant for a specific marker and time point was derived by subtracting the sample baseline mean from the participant's marker value at that time point and dividing this difference by the sample baseline SD. This composite score analysis represents an omnibus test of intervention efficacy across multiple (correlated) outcomes: rejection of the null hypothesis would suggest that the intervention (compared with controls) effected changes across components of the composite score. After this composite score analysis, we compared group differences for each of the outcomes; we present intervention results for the individual markers.

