Several secondary analyses were conducted. First, we evaluated intervention effects adjusted for baseline stratification variables (obesity status, employment status). Second, we evaluated group differences in outcomes between the 2 intervention arms. Third, we evaluated changes in physical activity (standing, stepping, light physical activity, and MVPA) by intervention arm. Fourth, we included an indicator variable for COVID-19 (yes or no) and evaluated 3-way COVID-19*group*time interaction (by likelihood ratio tests) to test whether changes in outcomes differed between participants with delayed 3-month assessment because of COVID-19 and those who received the original protocol. Fifth, we explored whether baseline hypertension status was an effect modifier for blood pressure and whether baseline glycemic status (HbA1c < or \geq 5.7%) was an effect modifier for glucoregulatory outcomes. We also excluded participants who self-reported having type 2 diabetes at baseline and repeated the LMM analysis. Last, we examined whether changes in MVPA altered the intervention effect estimates by including MVPA at baseline and 3 months as a time-varying covariate, and the MVPA*group interaction in the LMMs.

Gaussian link functions were used in the mixed models, and diagnostic plots were generated to evaluate model assumptions. Insulin, glucose, and HOMA2-IR were log-transformed to better approximate Gaussian distributions, and results were presented as geometric means with 95% CIs derived from model estimates (β coefficients) at baseline and at 3 months, along with mean (95% CI) within group changes. For the other outcomes, sedentary behavior measures, and blood pressure, mean (95% CI) at baseline and 3 months, as well as mean (95% CI) within-group change derived from model parameters (β coefficients), are presented. Treatment effects were calculated as the mean (95% CI) of the difference (compared with the control group) in absolute changes (for all outcomes) and percent changes (for log-transformed outcomes) from baseline to 3 months.

Analyses were implemented in the R statistical programming language, and LMMs were executed by R package nlme. All hypothesis tests were 2-sided. We used significance level $\alpha=0.025$ for the primary analyses to adjust for multiple comparisons (2 intervention groups versus control). No multiple comparison adjustment was made for secondary analyses.

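### The secondary MVPA-adjusted model mixes stable differences between women with change within a woman, so its group*time estimate can shift even when MVPA change has no effect

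*SAP*

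**What the plan says.** The SAP's Statistical Plan fits a linear mixed model in which "time (baseline, 3-month), group (active, control), and the group*time interaction were fixed-effect independent (categorical) variables". On the random part it says: "A subject-specific (random) intercept was included to model individual heterogeneity in outcomes". The group*time term is the estimand: "this difference of outcome changes between intervention and control arms represents the intervention effect".

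Among the secondary analyses, "we evaluated changes in physical activity (standing, stepping, light physical activity, and MVPA) by intervention arm", so whether the arms differ in MVPA change is treated as an open question. The last secondary analysis is the one at issue. Its stated aim is this: "we examined whether changes in MVPA altered the intervention effect estimates". The SAP describes the method as "including MVPA at baseline and 3 months as a time-varying covariate, and the MVPA*group interaction in the LMMs".

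The Protocol (Objective Measure of Sitting Time and STS Transitions) fixes the timing: "For 7 days before the baseline and 7 days before the 3-month final visit, participants are asked to wear the 2 devices". The second MVPA value is therefore measured after randomisation.

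Neither document separates between-woman from within-woman MVPA, uses MVPA change as the covariate, or states the assumptions needed to condition on a variable measured after randomisation.

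**The concern.** More active women may have better glucose or blood pressure values for reasons that have nothing to do with changing their activity during the trial. A random-intercept model with one MVPA level term per arm uses that between-woman association, as well as the within-woman one, to estimate the MVPA slope. The slope is then applied to the MVPA change in each arm, and this moves group*time. The movement can look like an effect of MVPA change when it reflects only stable differences between women.

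What is at stake is interpretation. The Protocol's Overview presents the programme as a move away from energy expenditure as the main route to benefit. This is the planned analysis that asks whether MVPA bears on the intervention effect. A spurious attenuation, or a spurious lack of one, would mislead on that question.

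**Working it through.** The documents give no figure for this analysis, so there is none to reproduce. The check asks how far group*time moves when MVPA change truly has no effect.

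**Inputs from the documents.** The model and estimand are those of the SAP's Statistical Plan. On size, the Protocol (Study Objectives) says "The study aims to enroll 405 postmenopausal women into the 3-month trial"; 405/3 = 135 per arm if allocation is equal, which is not stated.

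**Assumed inputs.** Outcome and MVPA are scaled to SD 1, with no missing data. Outcome intraclass correlation ρ = 0.7; MVPA intraclass correlation r = 0.6 or 0.7. The slope b of the outcome on a woman's usual MVPA level is -0.3 or -0.4. The arm difference D in mean MVPA change is 0.1 to 0.5 SD. The within-woman effect of MVPA and the intervention effect are both zero unless stated.

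**Step 1: how the slope moves group*time.** With both visits observed and fitted slopes s_A (active) and s_C (control), and mean MVPA changes m_A and m_C:

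adjusted group*time = unadjusted group*time − (s_A·m_A − s_C·m_C).

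With equal slopes s, the shift is −s·D.

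**Step 2: what the slope estimates.** In a two-visit random-intercept model, s = W·B + (1−W)·(within-woman slope), where

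- θ = (1−ρ)/(1+ρ) and W = θ(1+r)/[θ(1+r) + (1−r)];
- B = b·2r/(1+r), the slope on the two-visit mean.

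For ρ = 0.7 and r = 0.6: θ = 0.3/1.7 = 0.1765, so W = 0.2824/0.6824 = 0.414. When ρ = r, W = 0.50. Over ρ and r from 0.5 to 0.9, W runs from 0.14 to 0.86. The between-woman share is seldom negligible.

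**Step 3: size of the shift** (within-woman slope zero, ρ = 0.7). The simulated value is the planned estimate minus the unadjusted one.

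| r | b | B | W·B | D | −W·B·D | Simulated |
|---|---|---|---|---|---|---|
| 0.6 | -0.3 | -0.225 | -0.093 | 0.1 | 0.009 | about 0.01 |
| 0.6 | -0.3 | -0.225 | -0.093 | 0.3 | 0.028 | 0.024 − (-0.003) = 0.027 |
| 0.6 | -0.4 | -0.300 | -0.124 | 0.5 | 0.062 | 0.066 − 0.004 = 0.062 |
| 0.7 | -0.3 | -0.247 | -0.124 | 0.25 | 0.031 | 0.030 − (-0.001) = 0.031 |
| 0.7 | -0.3 | -0.247 | -0.124 | 0.5 | 0.062 | 0.067 − 0.004 = 0.063 |

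Formula and simulation agree. The least favourable corner of these inputs, r = 0.7 with b = -0.4 and D = 0.5, was not simulated; the formula gives 0.5 × 0.329 × 0.5 = 0.082.

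**Step 4: slopes that differ by arm.** With fitted slopes of -0.131 (control) and -0.131 + 0.135 = 0.004 (active), and the same 0.5 SD MVPA change in both arms, the shift is −(0.004 × 0.5 + 0.131 × 0.5) = -0.0675. The simulation gave -0.064 − 0.003 = -0.067.

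**Step 5: when nothing moves.** With equal MVPA change and equal slopes, or with no between-woman association, the simulated shift was zero to within 0.001 SD.

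**Step 6: what it does to inference** (600 runs per setting; ρ = r = 0.7, b = -0.3, D = 0.5). The standard error is 0.100. A nominal 5% test rejects 8.7% of the time; the simulation error of a 5% rate is √(0.05 × 0.95/600) = 0.9 percentage points. A true effect of -0.20 is estimated as -0.201 unadjusted but -0.138 in the planned model. MVPA then seems to explain 0.063/0.201 = 31% of the effect when it explains none. Over wider settings at D = 0.5, the shift runs from 0.034 (ρ = 0.9) to 0.112 (woman-level correlation -0.5), and rejection reaches 18% (r = 0.9).

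**Step 7: the split.** Enter each woman's mean MVPA and her deviation from it. With both visits observed, group*time is then what a regression of outcome change on arm, MVPA change and their product would give; the person mean drops out. In simulation, group*time stayed within 0.01 SD of the truth in every setting of this kind, with rejection of 3.5% to 6.5%. Those runs also carried a group interaction on the person mean. That term drops out of the change equation too, so omitting it does not alter the group*time estimate.

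Deviation from baseline does not do the same. It equals the full MVPA change at 3 months and so still differs between women. It left 0.018 of a 0.066 SD shift (27%).

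**The case against.** Five points can be made for the plan.

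- **No decision rule.** A reader might infer that the SAP will use this model to attribute the effect either to sitting or to exercise, or to declare the effect independent of MVPA. It says neither: it sets no threshold and no attribution rule, and says only that the matter was examined. This stands.
- **Not one slope.** A reader might infer a single MVPA slope. The model includes MVPA*group, so there is one per arm. This stands as description, but each arm's slope still blends the two associations, and the shift was 0.067 with or without the interaction.
- **The shift may be small.** MVPA is not the behaviour the arms target, and the Protocol's Overview describes sit-to-stand transitions as using little energy. If the arms hardly differ in MVPA change and the slopes are alike, little moves. This stands: at D = 0.1 the shift is about 0.01 SD, and all the Step 3 values are below one standard error.
- **The split does not cure confounding of changes.** This also stands. If unmeasured factors drive both MVPA change and outcome change, about 0.03 to 0.05 SD remained. In one set of runs the split did slightly worse than the planned model in the milder scenario (0.027 against 0.019) and better in the stronger one (0.048 against 0.077). In another set it did better in both (0.029 against 0.047; 0.048 against 0.095). The two biases can partly cancel in the planned model, but nobody can plan on that.
- **It is only secondary.** This limits the consequences. It does not make the model fit the question it is given.

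**Conclusion.** The point holds as a cheap improvement to one secondary analysis. The model asks about MVPA change but estimates slopes that partly reflect stable differences between women. The resulting shift in group*time is conditional. It needs a between-woman association of MVPA with the outcome, and either unequal mean MVPA change by arm or an MVPA change combined with unequal slopes.

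In the main settings simulated it is about 0.01 to 0.07 outcome SD against a standard error near 0.10; less favourable assumptions take it to about 0.11. The documents report no MVPA values, intraclass correlations or slopes, so the actual size is unknown and may be zero.

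A reader might infer that the trial's conclusion on efficacy is compromised. The documents do not support that: the primary group*time estimate contains no MVPA term and is untouched.

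**What to change.** Replace the MVPA level by two terms: each woman's mean MVPA over the two visits, and her deviation from that mean at each visit. Put the group interaction on the deviation. Do not use deviation from baseline, which keeps part of the blend.

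Report the adjusted group*time estimate as an exploratory association that assumes no confounding of MVPA change. State that some bias remains if that assumption fails, and keep the unadjusted difference in change as the intervention effect.

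The cost is one extra covariate, a sentence of labelling, and a loss of precision of about 1% to a few percent in this analysis. The SAP is written in the past tense, so in practice this is a refit of one model. Nothing in the primary analysis changes.

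### The primary contrasts are tested at a two-sided 0.025 level, but the same treatment effects are reported with 95% intervals, so test and interval can disagree for the two composites

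*SAP*

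**What the plan says.** All of this is in the SAP, under Statistical Plan.

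- **Parameter tested.** The primary test is of the group-by-time interaction in a linear mixed model. Of that contrast the SAP says: "this difference of outcome changes between intervention and control arms represents the intervention effect".
- **Primary outcomes.** The models are applied first to the glucoregulatory and blood pressure composites: "we first fit the aforementioned LMMs for 2 primary composite outcomes". The single markers come next: "After this composite score analysis, we compared group differences for each of the outcomes; we present intervention results for the individual markers". No significance level is given for them separately.
- **Level of the test.** "We used significance level $\alpha=0.025$ for the primary analyses to adjust for multiple comparisons", the comparisons being those of the two intervention arms with control. Also: "All hypothesis tests were 2-sided".
- **Level of the interval.** "Treatment effects were calculated as the mean (95% CI) of the difference (compared with the control group) in absolute changes (for all outcomes"), with percent changes added for the log-transformed outcomes.
- **Secondary analyses.** These carry no adjustment for multiple comparisons.

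Neither document provides a 97.5% or otherwise adjusted interval. Neither says that the 95% intervals are unadjusted, or that they should not be used to judge significance.

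**The concern.** The tested quantity and the reported treatment effect are the same parameter. The test is adjusted for having two intervention arms; the interval is not. A two-sided 95% interval excludes zero exactly when p is below 0.05, while the primary test needs p below 0.025. Between those limits the plan would produce a primary contrast that is not significant, displayed with an interval that lies wholly on one side of zero.

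The interval is the SAP's stated format for treatment effects, so many readers will judge the result from it. A reader who does so applies the 0.05 level per contrast and loses the adjustment that the SAP chose to make. The point does not depend on whether 0.025 is itself enough for two composites: the mismatch is there even if 0.025 is accepted as fully adequate.

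**Working it through.** **Inputs.** Test level 0.025, two-sided; two contrasts with control; interval level 95%; same parameter in both (all from the SAP, Statistical Plan). Assumptions: an overall level of 0.05, which the SAP does not state, and an approximately normal test statistic.

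**1. The plan's own figure.** Bonferroni for two contrasts: 0.05 / 2 = 0.025. This reproduces the stated level.

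**2. Critical values.**
- 95% interval excludes zero when |Z| > z(0.975) = 1.960.
- Test at 0.025 rejects when |Z| > z(0.9875) = 2.241.
- Ratio: 2.2414 / 1.9600 = 1.144, so the matching 97.5% interval is 14.4% wider. With t quantiles on 264 to 402 degrees of freedom (assumed), the ratio is 1.1449 to 1.1444, so the result does not rest on the normal approximation.

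**3. Example in the gap.** Take an estimate 2.1 standard errors (SE) from zero. Then p = 0.036, so the primary test does not reject.
- 95% interval: 2.1 ± 1.960 = 0.14 to 4.06 SE (excludes zero).
- 97.5% interval: 2.1 ± 2.241 = −0.14 to 4.34 SE (includes zero).

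**4. How often the two disagree, per contrast.** With d the true effect in SE units,

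P(conflict) = P(|Z + d| > 1.960) − P(|Z + d| > 2.241), Z standard normal.

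| True effect d (SE) | 95% interval excludes zero | Test at 0.025 rejects | Conflict |
|---|---|---|---|
| 0 (no effect) | 5.0% | 2.5% | 2.5% |
| 1 | 17.0% | 10.8% | 6.2% |
| 2.241 (50% power) | 61.1% | 50.0% | 11.1% |
| 2.241 + 0.842 = 3.083 (80% power) | 86.9% | 80.0% | 6.9% |

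Power here means power of the test at 0.025. At a given d, these rates do not depend on sample size or standard deviation.

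**5. Both contrasts for one outcome, no effect.** Assume equal arms and a shared control, which gives a correlation of 0.5 between the contrasts. By simulation, at least one test at 0.025 rejects in 4.6% of trials, at least one 95% interval excludes zero in 9.1%, and at least one conflict occurs in 4.8%. Judging by the intervals roughly doubles the error rate that the test level was chosen to hold (9.1 / 4.6 = 2.0).

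**6. Scope.** Two composites by two contrasts gives four treatment effects for which the mismatch is clear. The six single markers (insulin, glucose, HbA1c, HOMA2-IR, systolic and diastolic pressure) by two contrasts give twelve more, which are affected only if they too are tested at 0.025.

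**The case against.** The decision rule is not ambiguous. The SAP rests its conclusion on the interaction test and states the level; it nowhere says that significance is read from whether an interval excludes zero. A reader who applies 0.025 to the p value is not misled, and showing unadjusted 95% intervals beside an adjusted test is a recognised reporting choice. The sentence on 95% intervals also closes a paragraph about geometric means, log-transformed markers, blood pressure and sedentary behaviour, and does not name the composites.

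Much of this stands, and it limits the point. Three stronger readings that a reader might infer are not supported:

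- **That the primary test or its error rate is wrong.** The interval level changes neither the model, the estimate, the p value nor the rejection rule.
- **That the SAP fails to deliver joint 95% coverage.** It promises none. A 95% interval is correctly sized for its own single contrast.
- **That every treatment-effect interval is at the wrong level.** The SAP names the composites as primary and compares the single markers afterwards, without saying at what level. The Protocol, under Primary Outcomes, lists the markers themselves. If they are unadjusted, 95% intervals are consistent for them.

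What the objection does not remove is the gap for the composites. The interval sentence covers all outcomes, the composites are called primary outcomes, and no exception is made. The reporting choice would be defensible if it were stated, and it is not.

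**Conclusion.** The point holds as a mismatch in how the primary result is reported. For the two composites in both contrasts with control, the reported interval corresponds to a test at 0.05 while the test is made at 0.025. The two disagree only when p lies between 0.025 and 0.05: 2.5% per contrast with no effect, about 11% at 50% power and about 7% at 80% power, under a normal model.

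One further inference should be avoided. A p value of, say, 0.03 means that the null hypothesis is not rejected at 0.025; it does not mean that the plan declares the intervention ineffective. The harm is a contradictory display of the main result, which a reader could take as a positive finding.

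The conclusion assumes that the general wording on 95% intervals reaches the composites. It needs no figure for sample size, variance or planned power. The change should be made, because it concerns the reported primary result and is cheap.

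**What to change.** - For the treatment effect on each of the two composites, in each intervention-versus-control contrast, report a 97.5% interval. It then excludes zero exactly when p is below 0.025. If the primary level is later divided further, use the matching interval level.
- State whether the individual markers are primary at 0.025. If so, give their treatment effects 97.5% intervals as well; if not, keep 95%.
- Keep 95% intervals for arm means, within-group changes and secondary analyses, labelled as unadjusted.

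A lighter alternative is to keep 95% intervals throughout and state that they are unadjusted and that primary significance is judged only by p below 0.025. That explains the conflict but leaves it in the display, so matching intervals are preferable.

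The cost is a sentence or two in the SAP and a changed confidence level in the code. The intervals can be recomputed from the fitted models, with no new data or modelling. The primary intervals become about 14% wider; estimates, p values and test decisions do not change.

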## Measures and Outcomes

### Primary Outcomes

#### Glucose Regulation and Blood Pressure

The primary outcomes are glucose regulation and blood pressure assessed at baseline and at 3 months. Glucose regulation will be assessed by fasting plasma insulin and glucose, HbA1c, and HOMA-IR. Fasting blood (45 mL) is collected in EDTA and Li-Heparin vacutainers. Frozen processed samples will be stored in locked freezers at -80 °C. Plasma and whole blood samples will be used for glucose and HbA1c assays, and all analyses will include normalization and quality control standards. HbA1c is measured in whole blood in real time (DCA Vantage, Siemens). After blood sample collection is complete, fasting plasma glucose will be measured using the standard glucose oxidase method (YSI Bioanalyzer) and fasting plasma insulin will be measured using an immunoassay kit (Meso Scale Discovery, catalog #K151BZC). Standard curve samples and quality control replicates (minimum of 2 per plate) will be run on each assay plate. Linear dilution and spike-in controls will also be included in each assay run. Additional aliquots of samples will be stored at -80 °C should repeat analyses be required and also for future ancillary analyses. Blood pressure is measured using the Dinamap or Accutor 7 or Dinamap V100 blood pressure monitor after participants have rested while seated for at least 5 minutes. Measures are taken at least three times, and the mean of the second and third readings will be calculated.

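### The primary level of 0.025 adjusts for the two arms within each composite but not across the two composites, and neither the 95% CIs nor the marker comparisons are tied to it

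*SAP*

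**What the plan says.** The SAP's Statistical Plan introduces the composites with a stated purpose: "To reduce the chance of false positives, we first fit the aforementioned LMMs for 2 primary composite outcomes". One averages four Z scores (insulin, glucose, HbA1c, HOMA2-IR) and the other averages two (systolic and diastolic pressure). Each is an omnibus test over its own components: "rejection of the null hypothesis would suggest that the intervention (compared with controls) effected changes across components of the composite score".

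The decision rule is the interaction test: "A significant group*time interaction indicated that outcome changes differed between that intervention and the control arm". The final paragraph makes all tests two-sided and sets 0.025 "for the primary analyses to adjust for multiple comparisons (2 intervention groups versus control").

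The markers come next, without a condition: "After this composite score analysis, we compared group differences for each of the outcomes". Effects are presented with ordinary intervals: "Treatment effects were calculated as the mean (95% CI) of the difference (compared with the control group) in absolute changes".

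The protocol does not rank the two domains. Under Primary Outcomes: "The primary outcomes are glucose regulation and blood pressure assessed at baseline and at 3 months". Under Study Objectives, the hypothesis is that "participants in the 2 intervention arms will have greater improvements in glycemic control and blood pressure" than those in the control arm. Neither document gives an order of testing, a split of alpha or a statement of families across the two composites.

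**The concern.** Two composites and two arms make four primary tests, while the stated reason for 0.025 counts only the arms. The composites reduce false positives inside a domain, by replacing four tests or two tests with one. They do nothing about error between the domains. If the report claims efficacy from whichever composite rejects, the risk of a false claim is nearly twice what halving 0.05 suggests.

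Two related rules affect how results will be read. A 95% interval can exclude zero when the 0.025 test does not reject, so a reader going by the interval draws a different conclusion from the test. And if markers are compared whatever the composites show, a significant marker under a null composite can be read as a finding, which undercuts the purpose of testing the composites first.

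**Working it through.** **Inputs**
- Level 0.025, two-sided (SAP, final paragraph).
- 2 composites × 2 arms against control = 4 tests (SAP).
- 405 women in three arms (Protocol, Study Objectives). The allocation ratio is not stated; equal allocation is assumed, so 405/3 = 135 per arm. Two contrasts sharing a control then have correlation (1/n)/(2/n) = 0.5.
- The correlation *r* between composites is not given, so a range is shown.

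**1. The plan's own figure.** 0.05/2 = 0.025. This reproduces exactly. The 5% total is implied, not written.

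**2. Within one composite (two tests).** Upper bound 2 × 0.025 = 0.050. If independent, 1 − 0.975² = 0.0494. With the shared control, 0.0464-0.0467 by simulation. The arm adjustment does its job.

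**3. Across both composites (four tests).** Upper bound 4 × 0.025 = 0.100. If independent, 1 − 0.975⁴ = 0.0963. Simulating four jointly normal statistics under the global null (4 million draws, arm correlation 0.5), the chance of at least one rejection is:

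| *r* between composites | each test at 0.025 | each test at 0.0125 |
|---|---|---|
| 0 | 0.0908 | 0.0467 |
| 0.3 | 0.0890 | 0.0459 |
| 0.5 | 0.0854 | 0.0444 |
| 0.6 | 0.0824 | 0.0431 |
| 0.7 | 0.0787 | 0.0413 |
| 0.9 | 0.0666 | 0.0349 |

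With arm correlation 0.4 to 0.6 and *r* from 0 to 0.7, the 0.025 column runs from 7.6% to 9.3%. If one composite is truly affected in both arms, only the other's two tests can err, and the figure returns to 4.6-4.7%.

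**4. Interval against test.** The critical value is 1.960 for a 95% CI and 2.241 for a test at 0.025; the ratio is 1.144. Under the null, a 95% CI excludes zero without rejection in 0.05 − 0.025 = 2.5% of contrasts. The maximum is 11.2%, for a true effect near 2.1 standard errors. At least one of the four contrasts shows this conflict in 9.0-9.5% of null trials (*r* from 0.7 to 0).

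**5. Markers.** Six markers × 2 arms = 12 contrasts. Correlations among markers are not in the documents. Assuming 0.95 for insulin with HOMA2-IR, 0.2-0.7 among the other glucoregulatory pairs, 0.5-0.7 for systolic with diastolic and 0.1-0.2 across domains, the chance of any false marker claim at 0.025 is about 20% without a gate. It is about 8% if a marker counts only when its composite is rejected for that arm.

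**6. Price of 0.0125.** Assume a 0.25 SD effect and baseline to 3-month correlation 0.7 (neither is in the documents). SE = √(2/135 × 2 × 0.3) = 0.0943 SD, so the effect is 0.25/0.0943 = 2.652 SE. Power at 0.025 is Φ(2.652 − 2.241) = 66%; at 0.0125 it is Φ(2.652 − 2.498) = 56%. On a complete-case basis the fall is from 61% to 51% with 10% dropout (n = 121.5) and from 55% to 45% with 20% (n = 108). The SAP's mixed model keeps baseline-only records, which raises these dropout figures by roughly one point.

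**The case against.** The strongest reply is that the SAP says exactly what 0.025 adjusts for and promises nothing more. Glucose regulation and blood pressure are distinct domains, whether they form one family is a choice, and on the plain reading each composite is its own family, for which 0.025 is adequate. That stands, and so does the point that the 8-9% is conditional on the global null and on a claim resting on either composite. What remains is that both composites are called primary, neither is ranked, and nothing stops a claim from either one.

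A reader might infer three stronger things that the documents do not support:
- *That 0.025 is a miscalculation.* It is the correct Bonferroni level for two arms, and no sentence claims control across composites.
- *That success requires both composites in the same arm, which would make error across them a non-issue.* The only basis is a conjunction in the protocol's hypothesis; no joint decision rule is written.
- *That the markers have no significance level.* The protocol lists them as primary outcomes, the SAP describes their comparison directly after the composites, and its list of secondary analyses does not include it. The natural reading is that 0.025 applies. What is missing is a gate.

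It may also be said that 95% CIs beside an adjusted test are a reporting choice, since the test decides. That is correct as far as error goes: the mismatch inflates nothing. It still lets interval and test disagree on the primary contrasts, and it is cheap to remove.

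**Conclusion.** The point holds as a limit on what 0.025 controls. Error is about 4.6% within each composite and about 8-9% across both if either can support a claim. The larger figure assumes the global null, equal allocation and a between-composite correlation from 0 to about 0.65; it is about 6.7% at 0.9. It should not be read as the trial's unconditional error rate. Two rules work against the plan's stated aim of fewer false positives and should be changed: 95% CIs on contrasts tested at 0.025, and marker comparisons not conditioned on the composite. Moving the primary tests to 0.0125 is a trade-off, not a required correction.

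**What to change.** 1. Report the four primary composite contrasts with 97.5% CIs in place of 95% CIs, so that interval and test agree. Cost: intervals 14% wider.
2. Treat an individual marker contrast as descriptive unless its composite was rejected for that arm at 0.025. Cost: a real effect on a single marker that does not move its composite stays descriptive. The gate does not control error among the markers once their composite is rejected.
3. State that 0.025 controls error within each composite only, and claim no control across both. Add Holm-adjusted p-values over the four tests as a supporting result. Under the power assumptions above, Holm has 56% power per real effect if one is real, 58% if two are and 65-66% if all four are. As a supporting result it takes no power from the main test.

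Optional: replace 0.025 by 0.0125 if control across both composites is wanted. Family-wise error is then 4.1-4.7% (*r* from 0.7 to 0), at about 10 points of power in the assumed case, and 3-10 points over effects of 0.20-0.30 SD and correlations of 0.6-0.8 with no dropout. The matching intervals would be 98.75% CIs, 27% wider than 95% CIs.

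All of this re-reports existing model output and needs no new data. The SAP is written in the past tense; if results are already known, label each change post hoc and show it beside the 0.025 result.
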